4.2.2 Clinical Laboratory Evaluations

Blood and urine samples are collected and analyzed by a central laboratory. All laboratory results were standardized to Système International (S.I.) units. For all tables and figure summaries, only central laboratory data will be used. All data (including local laboratory data) will be included in listings.

In the case that multiple assessments map to the same visit, then the value at the scheduled assessment will be taken over any unscheduled assessments. If there are multiple unscheduled assessments, the assessment closest to the target study day will be used.

For the duration of the study, all safety laboratory assessments will be checked for abnormalities and measured against the NCI-CTCAE Version 5.0 for toxicities. The worst on-treatment assessment is determined by the value corresponding to the highest NCI-CTCAE Version 5.0 toxicity grade.

Hematology and biochemistry parameters with either a change of ≥ 2 in CTCAE Grade from baseline or a CTCAE Grade ≥ 4 will be flagged as markedly abnormal.

For the quantitative laboratory tests, the change from baseline value at each post-baseline visit will be calculated as the difference between the measurement obtained at the specific post-baseline visit and the baseline value.

In addition, quantitative test results at each visit will be categorized by the laboratory as 'Normal' (within the reference range) or 'Abnormal' (outside the reference range) according to the

Document: S:\Q_146\Q_03974\MEK-NF-201\Prog_Stat\Documentation\SAP\MEK-NF-201 SAP v1.0.0.docx
Author:

Statistical Analysis Plan

SpringWorks Therapeutics Protocol Number: MEK-NF-201

reference ranges specified in the laboratory manual. Abnormal results will be further classified as being 'Low' or 'High', depending on whether the result is below or above the reference range limits. For all abnormal values, clinical significance (as determined by the investigator) should be indicated.

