- In the event that a study site or participant is unable to complete a study visit or procedure due to restrictions caused by a public health emergency such as COVID-19, the following accommodations may be allowed temporarily with prior approval from the Medical Monitor / Sponsor. Any deviations from the study protocol due to a public health emergency should be documented in the source data and eCRF and reported to the IRB/EC in accordance with their reporting requirements.
 - If a study participant cannot attend a study visit onsite due to a public health emergency, they may be able to attend a local hospital/clinic or arrange for a telehealth or home healthcare visit.
 - Clinical laboratory assessments may be performed locally with results and local laboratory normal ranges entered into the eCRF.
 - Electrocardiograms may be performed locally. If ECGs are performed locally, ECG tracings should be collected and the Investigator (or designee) assessment should be documented. Every effort should be made to perform ECGs in triplicate; however, a single ECG will be allowed if necessary due to a public health emergency.
 - Study imaging (MRI) should be performed per the schedule in the SoAs at a qualified imaging facility; however, local imaging may be allowed if able to meet study imaging requirements (inclusive of required STIR sequence) and

with prior Sponsor approval. Local imaging will need to be uploaded for Central Imaging Review.

Table 7 Treatment Phase Key Study Visit Reminders

This table supplements the Treatment Phase SoA and highlights key study reminders. Refer to the SoA (Section 1.3) for a complete list of study assessments, and the study reference manual for study visit checklists which will include the recommended sequence of assessments for each study visit.

Screening Visit

The Screening visit may occur up to 45 days prior to the first dose of study treatment. However, to allow for the complete collection of the Baseline PRO assessments (Table 9) (which will begin 6 days prior to the Baseline visit), the minimum Screening period is 7 days. Screening period begins the day a participant signs the informed consent form.

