8.2.5. Clinical Safety Laboratory Assessments

All protocol-required laboratory assessments as defined in Section 10.2, must be conducted in accordance with the central laboratory manual and the SoA (Section 1.3, Section 1.4). The use of intravascular catheters should be considered when multiple blood draws will occur on the same visit.

The Investigator must review the laboratory report, document this review, and record any clinically relevant changes occurring during the study on the AE page of the eCRF. The laboratory reports must be filed with the source documents. Clinically significant abnormal laboratory findings are those which are not associated with the underlying disease, unless judged by the Investigator to be more severe than expected for the participant's condition.

All laboratory tests with abnormal values considered to be clinically significant during participation in the study or within 30 days after the last dose of study treatment should be repeated until the values return to normal or Baseline of the Treatment Phase or are no longer considered clinically significant by the Investigator or Medical Monitor. If such values do not return to normal/Baseline of the Treatment Phase within a period of time judged reasonable by the Investigator, the etiology should be identified, and the Medical Monitor notified.

If laboratory values from non-protocol specified laboratory assessments performed at the institution's local laboratory require a change in participant management or are considered clinically significant by the Investigator (e.g., SAE or AE or dose modification), then the results must be recorded in the eCRF. Additionally, local laboratory results are only to be used in extenuating circumstances to make a study treatment decision with approval from the Medical Monitor.

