6.12.1.2 Clinical Laboratory Parameters

All clinical laboratory parameters listed in Section 4.2.2 will be grouped by category and summarized by visit, with hematology, chemistry, urinalysis, and serology summarized separately. Absolute values and, where applicable, change from baseline for quantitative parameters will be summarized by the number of participants, mean, SD, median, minimum, and maximum values. Qualitative parameters will be summarized by absolute counts (n) and percentages (%). Percentages will be based on the number of participants with data.

Additionally, shift tables based on the NCI-CTCAE Version 5.0 toxicity grading scale will be presented for each laboratory parameter between pre-treatment and worst case on-treatment.

For parameters presenting both hyper- and hypo- NCI-CTCAE toxicities pre-treatment, both changes to lowest and highest on-treatment values will be presented as shift tables.

Additionally, an evaluation of drug-induced serious hepatotoxicity (eDISH) plots of max ALT versus max Bilirubin and max AST versus max Bilirubin will be produced by age cohort and overall. ALT/AST and Bilirubin will be displayed as multiple of the upper limit of normal (ULN) with lines denoting 2 x ULN for Bilirubin and 3 x ULN for ALT/AST.

Document: S:\Q_146\Q_03974\MEK-NF-201\Prog_Stat\Documentation\SAP\MEK-NF-201 SAP v1.0.0.docx

Author: Version 1.0.0, 02 Nov 2023

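### The eDISH plots and worst-on-treatment laboratory shift tables are restricted to central laboratory data, so a peak measured only locally is left out of them

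*SAP*

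**What the plan says.** SAP 4.2.2 sets the data source for every laboratory output: "For all tables and figure summaries, only central laboratory data will be used". It continues: "All data (including local laboratory data) will be included in listings". The same section defines the extreme value: "The worst on-treatment assessment is determined by the value corresponding to the highest NCI-CTCAE Version 5.0 toxicity grade".

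SAP 6.12.1.2 then specifies two kinds of output that rest on extremes:

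- Shift tables: "shift tables based on the NCI-CTCAE Version 5.0 toxicity grading scale will be presented for each laboratory parameter between pre-treatment and worst case on-treatment".
- eDISH: "plots of max ALT versus max Bilirubin and max AST versus max Bilirubin will be produced by age cohort and overall", with reference lines at 3 x ULN for ALT/AST and 2 x ULN for bilirubin.

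Neither is exempted from the central-only rule.

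The protocol provides for local results in three places:

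- **Section 8, opening bullets.** In a public health emergency, "Clinical laboratory assessments may be performed locally with results and local laboratory normal ranges entered into the eCRF".
- **Section 8.2.5.** Local results from assessments that the protocol does not specify must be recorded in the eCRF if they "require a change in participant management or are considered clinically significant by the Investigator".
- **Section 10.2 (Appendix 2).** Table 11 tests are done centrally. Where a local sample is needed because central results will not be ready in time, a central sample should be drawn at the same time.

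**The concern.** A central-only rule suits means and changes by visit: it gives one assay, one set of reference ranges and comparable values over time. A display of maxima has a different purpose, which is to show how bad things got for each participant. If the highest value was measured only at a local laboratory, the display shows a lower one.

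For eDISH this could move a participant out of the quadrant above 3 x ULN and 2 x ULN. Protocol 7.1.1 and 10.5 require ALT at or above 3 x ULN with bilirubin at or above 2 x ULN (more than 35% direct) to be reported as an SAE, as a possible Hy's Law case. The study report could then carry such an SAE beside an empty eDISH quadrant. In the shift tables, the participant's worst CTCAE grade would be too low.

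**Working it through.** No stated figure is at issue. The check sets the passages side by side and adds a short argument on direction.

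**1. Are the two displays under the rule?** Yes. eDISH is a figure and the shift tables are tables. SAP 4.2.2 covers all of both, and 6.12.1.2 adds no exception.

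**2. Can a local value be the only record of a protocol test?**

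- *Public health emergency, Protocol Section 8.* Yes. The provision covers the protocol's own laboratory assessments, so ALT, AST and bilirubin are included. Local normal ranges are captured, and no paired central sample is mentioned there.
- *Section 8.2.5.* Possibly. The sentence is limited to assessments that the protocol does not specify. This may mean other analytes, other times, or both. If it means other analytes only, it adds nothing to eDISH, because ALT, AST and bilirubin are in Table 11.
- *Section 10.2.* Here a central sample should exist, so the loss is small.

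**3. Which way can the error go?** Let C be a participant's central on-treatment values and L the local ones. Then

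max(C) ≤ max(C and L together),

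and the same holds for the highest CTCAE grade. With the pre-treatment value held fixed, leaving out L therefore leaves the eDISH position and the worst grade unchanged or makes them milder. It cannot make them more severe.

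**4. How much time lies between scheduled central draws?** From the study visit days in SAP Section 5.6:

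- Cycle 7 to Cycle 9: 239 − 183 = 56 days. The two-cycle spacing continues to Cycle 23.
- Cycle 24 Day 21 to Cycle 28 Day 15: 771 − 665 = 106 days.
- Cycle 28 to Cycle 32: 883 − 771 = 112 days.

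A rise and fall within such a gap is seen only if an extra sample is taken. Once an abnormality is known, Protocol 8.2.5 and 10.5 require repeat testing, so these gaps are upper limits on the unobserved time.

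**5. What would one case change?** The number of local-only peaks is not in the documents, so this is only a scale. With 100 participants, 0 cases is 0% with an exact two-sided 95% upper limit of 1 − 0.025^(1/100) = 3.6%. One case is 1% with an upper limit of 5.4%. In a single cohort of 50, one case is 1/50 = 2%.

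**6. A related ambiguity.** SAP 4.2.2 also prefers a scheduled result to an unscheduled one mapped to the same visit, and SAP 5.6 applies a similar preference for the nominal visit. Neither says whether this is done before the worst value is picked. If it is, an unscheduled peak could be lost even when it was measured centrally.

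**The case against.** The strongest reply is that nothing disappears from the report. Possible Hy's Law cases are SAEs, and Protocol 8.2.5 sends clinically relevant laboratory changes to the AE page. SAP 6.12.1.1 tabulates SAEs, TEAEs of Grade 3 or above, and TEAEs leading to interruption, reduction or discontinuation. Local values are listed. This stands: the gap is in particular displays, and a reader who inferred that liver events would be hidden from the safety report would be going beyond the documents.

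Three other strong inferences also fail:

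- *Local values as a group are selected for being abnormal.* The recording trigger in 8.2.5 selects in that way, but its reach to ALT, AST and bilirubin is unclear. Emergency-provision results replace central ones because of access, whatever their value.
- *The urgent liver repeats in Protocol 10.5 will be local-only.* That section names no laboratory. The repeats also follow a value already seen; if central ALT and bilirubin both met the trigger, the participant is already in the quadrant. A later, higher local value could still affect the shift table.
- *The markedly abnormal flags in SAP 4.2.2 omit local values.* The section says that all safety laboratory assessments are checked and graded, so the flags may already cover them.

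It is also fair that the emergency provision is temporary and needs prior approval, that Protocol 8.2.5 refers protocol-required tests to Section 10.2 with its paired central sample, and that Protocol 9.4.2 names no laboratory source, so the SAP contradicts nothing. Mixing assays has a real cost. These points limit how many participants could be affected. They do not justify a central-only rule for displays of maxima.

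**Conclusion.** The point holds in a narrow form. The plan bars local results from two displays built on extremes, and the protocol allows some protocol tests to be recorded only locally. The direction is certain: unchanged or milder. The size is unknown and may be zero. It depends on how often the emergency provision was used, how 8.2.5 was applied at sites, and how reliably paired central samples were drawn. No efficacy result is touched. The change is worth making because eDISH exists to summarise peak liver values, and a reader should not need the listings to correct it.

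**What to change.** In SAP 4.2.2 and 6.12.1.2:

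1. Limit the central-only rule to by-visit summaries.
2. For eDISH and the worst-on-treatment shift tables, use all on-treatment results in the database: central and local, scheduled and unscheduled. Express each local value against its own laboratory's ULN or LLN and flag it. Show the central-only version alongside. At minimum, add the central-plus-local version as a sensitivity display.
3. State that the preference for scheduled over unscheduled results (4.2.2, and the matching rule in 5.6) does not apply when selecting maxima or worst grades.
4. Keep local records without a reference range in the listings only.

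The cost is SAP wording, a little programming, and some between-laboratory variation, which scaling to local limits reduces but does not remove. No new data collection is needed: the emergency provision already records local ranges.

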4.2.2.1 Hematology

Hematology laboratory evaluations are performed at all scheduled visits in accordance with the SoA (Sections 1.3-1.4 of the protocol). The evaluated parameters are hemoglobin (HGB); hematocrit (HCT); platelet count; red blood cell count; red blood cell indices including mean cell volume, mean cell hemoglobin, and %reticulocytes; and white blood cell count with differential including neutrophils, lymphocytes, monocytes, eosinophils, and basophils.

4.2.2.2 Serum Chemistry

Serum chemistry laboratory evaluations are performed at all scheduled visits in accordance with the SoA (Sections 1.3-1.4 of the protocol). The evaluated parameters are aspartate aminotransferase (AST)/serum glutamic-oxaloacetic transaminase (SGOT), alanine aminotransferase (ALT)/serum glutamic-pyruvic transaminase (SGPT), total and direct bilirubin, gamma-glutamyl transferase (GGT), sodium, chloride, potassium, calcium, bicarbonate, inorganic phosphorous, alkaline phosphatase, creatinine, creatine phosphokinase (CPK), blood urea nitrogen (BUN), non-fasting glucose, uric acid, albumin, total protein, triglycerides, and total cholesterol.

4.2.2.3 Urinalysis

Urinalysis evaluations are performed at the time points specified in the SoA (Sections 1.3-1.4 of the protocol). The evaluated parameters are specific gravity, bilirubin, glucose, leukocyte esterase, nitrite, protein, urobilinogen, blood, ketones, pH, and microscopy (only if blood or protein is abnormal).

4.2.2.4 Serology

Serology is performed at screening. Tests are be performed for hepatitis B virus (HBV), hepatitis B surface antigen (HBsAg), hepatitis C virus (HCV) and hepatitis C antibody.

4.2.3 Electrocardiogram (ECG) Evaluations

Triplicate 12-lead electrocardiogram (ECG) evaluations are performed at the time points specified in the SoA (Sections 1.3-1.4 of the protocol). At each visit, three ECG assessments are performed in succession, approximately 3 minutes apart, these triplicate recordings are averaged to give the result for a given visit and parameter. In the case that not all ECG assessments were recorded, the average of the recording(s) taken will be used. At the C1D1 visit measurements are taken both pre-dose and post-dose.

Table 9 presents the quantitative and qualitative ECG parameters that were collected.

Table 9: ECG Parameters

ECG Parameters (Unit)
Conduction Times
Heart rate (bpm)
RR Interval (msec)
PR Interval (msec)

Document: S:\Q_146\Q_03974\MEK-NF-201\Prog_Stat\Documentation\SAP\MEK-NF-201 SAP v1.0.0.docx

Author:

QRS Interval (msec)
QT Interval (msec)
QTc Interval (msec)
QTcF Interval (msec)

For the quantitative ECG parameters, the change from baseline value at each post-baseline visit will be calculated as the difference between the measurement obtained at the specific post-baseline visit and the baseline value.

4.2.4 Echocardiograms

Echocardiograms are performed to assess left ventricular ejection fraction (LVEF) (%) in accordance with the SoA (Sections 1.3-1.4 of the protocol).

4.2.5 Vital Signs Evaluations

Height and weight are measured at screening, baseline visit (C1D1), and Cycles 3, 7, 11, 15, 19 and 23 for the Treatment Phase, and Cycle 28 and every 4 cycles after that during the study (I.e. LTFU phase). All other vital signs evaluations were performed at all visits described in accordance with the SoA (Sections 1.3-1.4 of the protocol). The following variables were collected:

- Height (cm)
- Weight (kg)
- Systolic blood pressure (SBP) (mmHg)
- Diastolic blood pressure (DBP) (mmHg)
- Respiratory rate (breaths/min)
- Pulse rate (beats/min)
- Body temperature (degrees C)

In addition to the collected variables, the following variables will be derived at all visits with recorded height and weight data:

 BSA (m²) will be calculated according to the Du Bois formula as: BSA (m²) = 0.007184 × Weight(kg)^{0.425} × Height(cm)^{0.725}.

For each variable the change from baseline value at each post-baseline visit will be calculated as the difference between the measurement obtained at the specific post-baseline visit, and the baseline value.

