- 18. Range of motion assessment (Section 8.1.5) will be assessed for participants with a target PN that causes motor dysfunction or weakness. Must be done prior to first dose of study treatment at the Baseline visit. Range of motion assessment at the early termination (ET) visit only required if not performed within the past 1 month.
- 19. 6-minute walk test (Section 8.1.7) will be conducted if a target PN causes airway dysfunction or lower extremity motor dysfunction. A practice 6-minute walk test must be conducted during Screening. Must be done prior to first dose of study treatment at the Baseline visit. The 6-minute walk assessment at the early termination (ET) visit is only required if not performed within the past 1 month. Heart rate and blood pressure will be collected after completion of the 6-minute walk test in accordance with the study reference manual.
- 20. Photography of PN (Section 8.1.4) will be performed if target PN and/or its effects are visible and amenable to photography. Baseline photographs should be present at the time of follow-up photography to allow for the most accurate positioning and setting replication. Photography assessment at the early termination (ET) visit only required if not performed within the past 1 month. Refer to study reference manual for details.
- 21. Bone plate radiographs: (Section 8.2.9) For all participants 2 to 17 years of age, radiographs of the distal femur and proximal tibia will be obtained at Baseline. If the Investigator determines that the physes are open, these participants will undergo radiographs at the schedule specified in the SoA.
 - 21a. Bone plate radiograph at ET visit only required if not performed within the past 6 months.
- 22. Patient reported outcomes (PROs) (Section 8.1.2): Refer to Table 9 for the PROs and Age Range Scale. Participants will complete the questionnaires using an electronic PRO device (ePRO) for all questionnaires except for the PedsQL and P-OMAQ, which will be paper questionnaires. The paper PedsQL should always be the first PRO administered at the visit. During study visits, the PROs should be the first assessment to minimize participant bias.

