Participants who complete Cycle 24 of the Treatment Phase and did not meet withdrawal criteria (Section 7) are eligible to participate in the LTFU Phase. Eligible participants will continue taking the last dose assigned in the Treatment Phase (approximately 2 mg/m² BID [maximum dose of 4mg BID]) of PD-0325901 (mirdametinib; open-label study treatment), on an intermittent (3 weeks on/1 week off) dosing schedule in 28-day cycles. Participants will remain in the LTFU Phase until a withdrawal criterion is met as described in Section 7 or mirdametinib is commercially available. Refer to the schedule of activities ([SoA] Section 1.4) for the required assessments for the LTFU Phase.

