8.2.9. Radiography

For all participants 2 to 17 years of age, radiographs of the distal femur and proximal tibia will be obtained at Baseline. If the Investigator determines that the physes are open, these participants will undergo a radiograph in accordance with the Treatment Phase SoA (Section 1.3) to monitor for changes in physeal growth plates.

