9.4.2. Safety Analyses

All safety analyses will be performed on the Safety Population.

Endpoint	Statistical Analysis Methods
Safety Endpoints	The safety and tolerability of mirdametinib (PD-0325901) will be evaluated by means of study drug-related adverse event reports, physical examinations, and laboratory safety evaluations. National Cancer Institute CTCAE Version 5.0 will be used for grading of adverse events. Investigators will provide their assessment as related to treatment (definite, probable, or possible relationship).
	The incidence of treatment-emergent adverse events, SAEs, adverse events of at least Grade 3 in severity, study drug-related adverse events, and adverse events leading to withdrawal of study drug will be summarized. Treatment-emergent adverse events will be those that start or worsen on or after the first day of study drug through 30 days after the last dose of study drug; related adverse events will be those with an Investigator determination of related to treatment.
	Laboratory data will be analyzed by summary statistics over time, as well as by shift tables based on NCI CTCAE Version 5.0 grades of severity. In addition, ECG intervals will be summarized by visit. The number and percentage of participants who have a post-Baseline QTcF between 450 and 480, > 480, and > 500, as well as the number and percentage of participants who have a change from Baseline in QTcF of < 30, 30 to 60, and > 60 will be summarized.

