4.2 Safety Measures

The safety measures in this study include assessing treatment-emergent adverse events (TEAEs) (additionally by dose formulation), electrocardiograms (ECGs), Echocardiograms, clinical laboratory evaluations, vital signs assessments, and ophthalmic measurements. The endpoints described in this section will be analyzed according to the analysis methods described in Section

Document: S:\Q_146\Q_03974\MEK-NF-201\Prog_Stat\Documentation\SAP\MEK-NF-201 SAP v1.0.0.docx
Author:

6.12.1. For all applicable safety measures, the baseline value will be defined as the most recent assessment taken on or before the treatment start date, unless otherwise specified.

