6.12.1.5 Vital Signs

Absolute value and change from baseline for all vital signs parameters as listed in Section 4.2.5 will be summarized by visit. Continuous variables will be summarized by the number of participants, mean, SD, median, minimum, and maximum values. Categorical variables will be summarized by absolute counts (n) and percentages (%). Percentages will be based on the number of participants with data.

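### Children's height is summarised only in raw centimetres pooled over ages 2 to 17, and the growth-plate films have no planned output

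*SAP*

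**What the plan says.** **Height.** SAP 4.2.5 lists height in cm among the vital signs and defines its change: "For each variable the change from baseline value at each post-baseline visit will be calculated as the difference between the measurement obtained" at that visit and the baseline value. SAP 6.12.1.5 then plans: "Absolute value and change from baseline for all vital signs parameters as listed in Section 4.2.5 will be summarized by visit". Under SAP 5.1.2 continuous variables are shown by age cohort unless stated otherwise, so ages 2 to 17 and both sexes fall into one column. BSA is the only derived body-size variable; no z-score, percentile or growth velocity is defined.

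**Radiographs.** For all participants 2 to 17 years, protocol 1.3 (footnote 21) says that "radiographs of the distal femur and proximal tibia will be obtained at Baseline". If the investigator finds the physes open, films are repeated at Cycle 13, Cycle 24 and early termination (the last only if none was taken in the past 6 months). Protocol 8.2.9 gives the purpose: "to monitor for changes in physeal growth plates".

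**Planned safety outputs.** Apart from treatment-emergent adverse events, SAP 4.2 lists "electrocardiograms (ECGs), Echocardiograms, clinical laboratory evaluations, vital signs assessments, and ophthalmic measurements". Protocol 9.4.2 names "study drug-related adverse event reports, physical examinations, and laboratory safety evaluations" and adds ECG summaries. Neither mentions the films, and SAP 6.12.1.1 to 6.12.1.7 contain no summary, shift table or listing for them.

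**Long-term phase.** Protocol 4.1 sets no fixed end: "Participants will remain in the LTFU Phase until a withdrawal criterion is met as described in Section 7 or mirdametinib is commercially available". The schedule in protocol 1.4 keeps height but has no films.

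**The concern.** A growing child has a positive height change whether growth is normal or slowed. The size of a normal change depends on age and sex, and the trial has no control arm. A mean in centimetres over ages 2 to 17 therefore has no value against which a shortfall could be seen. Absolute height has the same weakness.

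The films are the one scheduled assessment aimed at the growing skeleton, yet no output shows how many children had open physes, how many had follow-up films, or what those films showed. Other specialised safety assessments do get their own outputs: LVEF has a shift table, QTcF has categories and intraocular pressure has a summary.

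At stake is a descriptive safety question specific to children, in a study where dosing may continue without a set end.

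**Working it through.** The documents give no power, threshold or expected value for growth, so there is no plan figure to reproduce. The check asks what the planned height output would show if growth were slowed.

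**Inputs**
- Middle (fourth of seven) height column at each age, protocol Tables 12 (girls) and 13 (boys).
- Treatment Phase: 24 cycles × 28 days = 672 days. Two years = 730.5 days. Ratio 672 / 730.5 = 0.920.
- Assumptions: the child starts on the middle column, the tabulated gain is linear within each two-year interval, and slowed growth means 50% of the tabulated gain (75% and 25% as a range). The fractions are illustrative and do not come from the documents.

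**Formulas**
- Expected gain = (height at age + 2 − height at age) × 0.920
- Raw change under slowing = fraction × expected gain

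| Start age | Girls, two-year gain (cm) | Expected, 24 cycles | Half rate | Boys, two-year gain (cm) | Expected, 24 cycles | Half rate |
|---|---|---|---|---|---|---|
| 2 | 104.5 − 91.1 = 13.4 | 12.3 | +6.2 | 105.9 − 92.1 = 13.8 | 12.7 | +6.3 |
| 4 | 118.4 − 104.5 = 13.9 | 12.8 | +6.4 | 118.9 − 105.9 = 13.0 | 12.0 | +6.0 |
| 6 | 130.6 − 118.4 = 12.2 | 11.2 | +5.6 | 131.0 − 118.9 = 12.1 | 11.1 | +5.6 |
| 8 | 141.0 − 130.6 = 10.4 | 9.6 | +4.8 | 141.3 − 131.0 = 10.3 | 9.5 | +4.7 |
| 10 | 154.8 − 141.0 = 13.8 | 12.7 | +6.3 | 152.7 − 141.3 = 11.4 | 10.5 | +5.2 |

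The expected gain is 9.5 to 12.8 cm. Raw change is +7.1 to +9.6 cm at 75% of expected growth, +4.7 to +6.4 cm at 50%, and +2.4 to +3.2 cm at 25%. It is positive throughout. Odd starting ages change only the lower end: the smallest two-year gain is then 10.1 cm (boys, 9 to 11), giving 10.1 × 0.920 = 9.3 cm expected and 4.6 cm at half rate.

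**At the SAP's own last Treatment Phase height visit.** SAP 4.2.5 stops at Cycle 23, which SAP Table 10 places on day 631, 630 days after first dose. With 630 / 730.5 = 0.862, the half-rate change in the same children is 10.3 × 0.862 / 2 = 4.4 cm to 13.9 × 0.862 / 2 = 6.0 cm. The conclusion is the same.

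**Spread of normal growth.** Normal expected gain differs by 12.8 − 9.5 = 3.3 cm between these starting ages and sexes. Growing at 75% of the expected rate costs 2.4 to 3.2 cm. A slowing of a quarter is thus no larger than the difference between normal children of different ages. Participants near 17 probably gain close to nothing (assumption), which widens the spread further.

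**What an age- and sex-referenced measure would show.** A girl starting at age 4 at 104.5 cm and growing at half rate reaches 104.5 + 6.4 = 110.9 cm after 24 cycles. The middle column is then 104.5 + 13.9 × 0.920 = 117.3 cm, so she is 6.4 cm short. The second-lowest column is 98.8 + (111.8 − 98.8) × 0.920 = 110.8 cm. She has dropped from the fourth column to about the second, while the planned table records +6.4 cm.

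**Height visits side by side.** SAP 4.2.5 has screening, baseline, Cycles 3, 7, 11, 15, 19 and 23, then Cycle 28 and every 4 cycles. The protocol 1.3 schedule also has Cycles 5, 9, 13, 17, 21 and 24, early termination and safety follow-up. The SAP list therefore omits the end-of-phase and early-termination heights.

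**The case against.** The strongest case on the other side has five parts.

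- **A route for findings exists.** Protocol 10.3.1 counts abnormal radiological scans and vital signs as adverse events when the investigator judges them clinically significant. These would enter the adverse event tables across both phases, and the DMC reviews aggregate safety. This stands: a reader might infer that growth-plate change would go unseen, and the documents do not support that. The route gives no denominator of children with open physes and follow-up films, however, and depends on individual judgement.
- **Slowed growth is not a named risk.** A reader might infer that the protocol identifies it. It does not: protocol 8.2.9 speaks of changes in growth plates, the benefit/risk section, the objectives and the special-interest events are silent on growth, and footnote 5 of protocol 1.3 says height is measured to monitor BSA. The link from the films to height is a reasonable inference and no more. The missing output for the films needs no such inference.
- **Height is not analysed only as change.** Absolute height is summarised as well. This stands, but it is equally unadjusted for age and sex.
- **The question is not lost.** A reader might conclude that the trial cannot examine growth. Height, age and sex are collected, so standardised height can be derived at any time. What is missing is the plan to do so.
- **Coded film results may not exist.** The documents describe only the investigator's judgement of whether physes are open. They describe no grading, central reading or data field for a new finding. This stands and limits what can be asked for.

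The absence of films in long-term follow-up is a protocol design matter that a SAP change would not alter.

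**Conclusion.** The point holds as a gap in descriptive safety analysis. Height in participants 2 to 17 is planned only as absolute value and change in centimetres, pooled over age and sex. At an assumed half of the tabulated growth rate, the output over 24 cycles would still show a gain of about 4.7 to 6.4 cm. The growth-plate films that the protocol requires have no planned summary or listing.

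The size rests on the middle columns of Tables 12 and 13, which cover ages 2 to 12 only, on linear interpolation, and on the assumed growth fractions. It is an illustration, not an estimate of any drug effect. The change is worth making because it is cheap and supplies the reference value that a single-arm cohort lacks. No primary or secondary efficacy conclusion depends on it.

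**What to change.** 1. In SAP 4.2.5 and 6.12.1.5, for participants under 18 at baseline, derive an age- and sex-standardised height z-score against a growth reference named in the SAP. Summarise its change from baseline by visit through both phases, next to the existing raw summaries.
2. Reconcile the height visits in SAP 4.2.5 with the protocol 1.3 schedule, so that Cycles 5, 9, 13, 17, 21 and 24, early termination and safety follow-up are covered.
3. Add the films to SAP 4.2 and 6.12.1. List the results as recorded. Where the data allow, count participants with open physes at Baseline who have a reported growth-plate change at Cycle 13 and at Cycle 24 or early termination, with the number who had a film at each as denominator.

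A threshold such as a fall of 1 z-score, and a split by physis status, are optional. Neither has a basis in the documents, and a split would thin a cohort of about 50.

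The cost is SAP wording, programming and the choice of reference. Height, age, sex and the films are already scheduled, so no procedure is added. Counting film findings may need some retrospective coding if results were not captured in a structured form; the listing does not depend on that.
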